BMI inclusion criteria, individuals will undergo further screening including the expanded Short Physical Performance Battery (expSPPB), a cognitive screen (Montreal Cognitive Assessment, MoCA³¹), physical activity assessment (the Community Healthy Activities Model Program for Seniors [CHAMPS] questionnaire³²) to ensure no regular participation in resistance exercise or high-volume aerobic training in the past 6 months, a depressive symptom screening test (Center for Epidemiological Studies-Depression, CES-D³³), a weight loss readiness questionnaire, and, if still eligible, a medical history, a comprehensive review of medications, blood pressure, and a fasting blood draw for a metabolic screening panel and complete blood count (CBC) to exclude those with recent history of coronary heart disease, cancer, liver or renal disease, severe pulmonary disease, gross physical impairment, uncontrolled hypertension, uncontrolled diabetes, or any contraindications to exercise. Participants will also be given a 4-day food record to complete. If still eligible, a second in-clinic screening visit will be scheduled for a GXT (to rule out any contraindications for supervised exercise) and DXA scan (to rule out osteoporosis) and to collect the 4-day food record. Participants will also do a taste test of the protein and carbohydrate supplements to ensure that they are willing to consume the product during the intervention and complete a perceived weight loss readiness questionnaire.

Table 1. Inclusion/exclusion Criteria

Criteria	Inclusion	Exclusion	Assessment
Age	65-85 years		Self-report
Obesity status	BMI: 30-45 kg/m ² or BMI 27.0 – <30.0 AND at least ONE of the following risk factors: 1) elevated waist circumference (>35 inches in women, >40 inches in men) 2) diabetes, 3) hypertension, 4) dyslipidemia, 5) or other obesity-related comorbidities: clinically manifest coronary artery disease [e.g., history of MI, angina pectoris, coronary artery surgery, coronary artery procedures (e.g., angioplasty) if not within the past year], other atherosclerotic disease [e.g., peripheral arterial disease, abdominal aortic aneurysm, symptomatic carotid artery disease if not within the past year], sleep apnea, or osteoarthritis of the knee or hip.		Measured on scale 1)Measured with tape measure 2-4) Self-report and treatment 5) Self-report
Weight loss		Weight loss (≥5%) in past 6 months	Self-report

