Physical activity status	No regular (moderate intensity or greater) resistance training and/or aerobic exercise (>20 mins/d) for past 6 months		Self-report
Functional status	expSPPB <2.50	Dependent on cane or walker	expSPPB / self-report
Cognitive status		Cognitive impairment (MoCA score <22)	Questionnaire
Orthopedic status	No contraindications for safe and optimal participation in exercise training	Severe arthritis, or other musculoskeletal disorder Joint replacement or other orthopedic surgery in past 6 months	Self-report
Co-morbidity/health status	Approved for participation by Medical Director ([name])	Uncontrolled resting hypertension (>160/90 mmHg); Uncontrolled diabetes (HbA1c ≥8.0%) Current or recent past (within 1 year) severe symptomatic heart disease,	BP measurement HbA1c blood test Self-report

Table 1. Inclusion/exclusion Criteria

Criteria	Inclusion	Exclusion	Assessment
		uncontrolled angina, stroke, chronic respiratory disease requiring oxygen; uncontrolled endocrine/metabolic disease; neurological or hematological disease; cancer requiring treatment in past year, except non-melanoma skin cancers; liver or renal disease; or clinically evident edema Unstable Severe Depression Serious conduction disorder, uncontrolled arrhythmia, or new Q waves or ST-segment depressions (>3 mm at rest or ≥ 2 mm with exercise) Abnormal kidney function (eGFR <30 based on serum creatinine, age, gender, and race) Anemia (Hb<13 g/dL in men; <12 g/dL in women) Drug abuse or excessive alcohol use (>7 drinks/week women; >14 drinks/week men) Use of any tobacco or nicotine products in the past year Osteoporosis (T-score ≤ -2.5 on hip or spine scan)	Questionnaire (CES-D) GXT Metabolic panel CBC Self-report Self-report DXA
Medication / supplement use		Regular use of growth hormone, anabolic steroids/hormones, sex steroids (testosterone; estrogen – oral or patch) or corticosteroids (medications that can affect muscle mass/strength and/or bone) Osteoporosis medication Protein supplements (and unwilling to stop using for duration of study) Weight loss medications or procedures	Self-report and medication inventory
Research participation	Willing to provide informed consent Agree to all study procedures and assessments Willing to consume protein/CHO supplements for up to 18 months Able to provide own transportation to study visits and intervention sessions	Current participation in another intervention study	Self-report Taste test

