Baseline visit 2 (BV2) will take place approximately 1 week after the BV1 visit in the morning (after an 8 hour overnight fast). Participants will have their weight and blood pressure measured. Then participants will have their resting metabolic rate (RMR) assessed for the purpose of estimating each person's baseline calorie level. Participants will also undergo tests to assess arterial stiffness, including aortic augmentation index (AIx) and arterial wave reflection magnitude. Participants will then have blood drawn for glucose, insulin, HbA1c, lipids, and storage. The first of three 24-hr dietary recalls will be administered to introduce and train the participant for the procedures used in subsequent 24-hr dietary recalls done by phone (in the event that scheduling precludes

administration of the first 24-hr dietary recall in person, the participant will be given written instructions and the first 24-hr dietary recall administered by phone). Two additional 24-hr diet recalls will be administered by phone following BV2 but prior to the participant's first intervention visit. (24-hr diet recalls may be started at BV1 for some participants to ensure they are completed prior to the start of intervention.) Following all fasting measures, participants will be given a snack. Medical history and current medications and dietary supplements will be reviewed. The 24-hour urine sample will be collected to measure urinary nitrogen and creatinine for estimating dietary protein intake and for storage.

Randomization/first intervention visit. Due to the group nature of the diet classes, participants will be randomized in waves with all participants starting intervention in a given week. The study interventionist will check to see which intervention group the participant is randomized to at their first meeting with each eligible participant during the first week of each wave's intervention.

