excluding intermuscular fat, will also be assessed and used to quantify IMAT. CT slices within 15 mm centered at the L4-5 level will be selected to quantify SAT and VAT. Quantitative measures of thigh muscle and adipose tissue volume and CT attenuation values will be obtained with the GE Healthcare, Advantage Windows 4.2 Volume Viewer (Waukesha, WI). This software provides the ability to determine tissue-specific thresholds based on CT number (-190 to -30 Hounsfield units for fat) and volumetrically measure complex structures using semi-automated techniques such as edge attraction and volume rendering. The same CT reading technician will analyze all scans. Daily calibration scans are obtained according to the manufacturer's recommended procedure.

Tertiary outcomes (assessed at baseline and at 6- and 18-month follow-up [Arterial Stiffness at baseline and 6-month follow-up only]):

Bone mineral density. DXA will be used to analyze bone mineral density (BMD) using specific scans of the anterior-posterior (AP) spine (L1-L4) and proximal femur.

Volumetric bone mineral density, morphometry and strength. Helical CT scans of the lumbar spine and hip/pelvis will be used to measure volumetric bone mineral density, structure and strength of the lumbar spine (L1-L5), total hip and proximal femur. The scan coverage for the lumbar spine will be from the top of L1 through the base of L5. The hip/pelvis scan will cover the region from the superior acetabulum to mid-femur. The mid-femur position will be defined as the midpoint between the superior aspect of the greater trochanter and the inferior aspect of the lateral condyle. To locate the mid-point, an anterior-posterior scout of the entire femur will be obtained. The same Mindways bone mineral phantom (Mindways Software, Inc., Austin, TX) will be imaged in every scan.

Lipoprotein lipids. The lipoprotein lipid assays will be performed by LapCorp.

Fasting glucose and insulin. Fasting glucose and insulin assays will be performed by LapCorp. An estimate of insulin sensitivity by the homeostasis model assessment (HOMA) score will be calculated with the formula: fasting plasma insulin (μ U/ml) \times glucose (mmol/l)/22.5.⁵¹ Glucose and insulin area under the curve will be determined using Tai's model: $\frac{1}{2} \times 30 \times (y_{0\text{min}} + 2y_{30\text{min}} + 2y_{60\text{min}} + 2y_{90\text{min}} + y_{120\text{min}})$, where y represents insulin or glucose values at the different time points.⁵²

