weight per minute (ml/kg bwt/min) and per kg of lean mass per minute (ml/kg LM/min). Two of the following 3 criterion must be met for a test to be considered valid (or the test will be repeated): 1) plateau in oxygen consumption with increasing workload (< 200 ml/min); 2) respiratory exchange ratio ≥ 1.10 ; and 3) maximal HR within 90% of age-predicted maximal HR ($208 - [0.7 \times \text{age}]$).

Resting metabolic rate (RMR) will be measured at baseline for prescribing calorie deficits during the weight loss intervention and at 6 months for prescribing weight maintenance diets. The test will be conducted in the morning after an overnight fast using indirect calorimetry. Upon arrival, participants are asked to rest quietly for 20-30 minutes before testing. Measurement of oxygen consumption and carbon dioxide production are collected continuously for up to 30 minutes and RMR is calculated using the Weir equation.⁵⁹

Demographic characteristics (age, sex, race, education, and socio-economic status) will be ascertained by questionnaire at the screening visit.

A **weight loss readiness** questionnaire will assess participants' motivation, commitment, and any barriers to attending the 6-month weight loss intervention at the screening visit.

Medical information regarding **co-morbidities** will be ascertained at the screening visit. We will record **medication and supplement use** at baseline and at 6-, 12- and 18-month follow-up. Participants will be asked to bring in medications and dietary supplements for a "brown bag" review. The medication form will specifically ask about the use of protein supplements, anti-inflammatory agents, and sex steroids or corticosteroids.

Cognitive function will be assessed at screening using the Montreal Cognitive Assessment (MoCA),³¹ participants must score ≥ 22 to be eligible. We will also assess psychomotor speed, attention, and working memory using the Digit Symbol Substitution Test (DSST) at baseline and at 6- and 18-mo follow-up. Participants are given a series of numbered symbols and then asked to draw the appropriate symbols below a list of random numbers. The score is the number of correctly made matches in 2 minutes (120 seconds).

Initial body weight and change in body weight: Participants will be weighed, without shoes or heavy clothing, on a standard, calibrated scale weekly during the 6-month weight loss intervention and at the baseline, 6-, 12- and 18-month follow-up visits.

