Data analysis: Initial analyses will follow the “intent-to-treat” principle in which data from all randomized participants are analyzed according to their randomized groups. Analysis of covariance (ANCOVA) will be used for both primary and secondary aims to compare the group effect on change in expSPPB and muscle strength (primary aim) and weight loss maintenance, total and appendicular lean mass and fat-to-lean mass ratio, and thigh muscle volume and inter-muscular adipose tissue (IMAT) (secondary aim) at 18 months. Group contrasts will be constructed and tested within each model. ANCOVA will also be used to compare physical function, weight and body composition at 6 months. To explore whether differences in lean mass mediate the effect of a higher protein diet during and subsequent to weight loss on physical function, change in lean mass will be added to the ANCOVA models to assess whether the intervention effect is reduced or eliminated as an ad hoc mediation analysis. To compare the exploratory outcomes (bone mineral density and cardiometabolic risk factors) at 6 and 18 months, ANCOVA with repeated measurements will be used, and correlations between 6 and 18 months taken into account using a compound symmetry covariance structure. All models will be adjusted for the baseline measure, age, gender, and race.

Factors that may influence the measured responses to the interventions (e.g., initial body weight or composition, changes in weight, physical activity, etc.) will be evaluated and possibly included in secondary analyses. We will also consider conducting analyses adjusted for intervention process measures (such as dietary intake, average attendance at diet and exercise sessions, and protein intake/urinary nitrogen) to examine the extent to which these contribute to the outcomes.

Planned sensitivity analyses to assess the impact of COVID19: Because of the potential impact of COVID19 on intervention delivery and follow-up assessments, we plan to conduct several sensitivity analyses:

- 1) Exclude Wave 13 and 14 participants (n=26) whose intervention was interrupted by the COVID19 research pause on March 13, 2020, and who completed the last ~2 and ~4 months, respectively, of the exercise portion of the 6-month intervention on their own while attending the diet portion of the intervention remotely (via phone).

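### Fasting insulin and HOMA are to be analysed in all randomised participants with no restriction for insulin use, although treated diabetes is eligible, and HOMA is labelled as sensitivity when it rises with resistance

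*Protocol*

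**What the plan says.** **Outcome.** Under Tertiary outcomes (Fasting glucose and insulin), the protocol says "An estimate of insulin sensitivity by the homeostasis model assessment (HOMA) score will be calculated with the formula" insulin (μU/ml) × glucose (mmol/l) / 22.5. No subset is named. At the second baseline visit, "Participants will then have blood drawn for glucose, insulin, HbA1c, lipids, and storage"; glucose and insulin are drawn again at 6 and 18 months.

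**Eligibility.** Protocol Table 1 (Obesity status) lists "2) diabetes, 3) hypertension, 4) dyslipidemia" among the risk factors that qualify a person with BMI 27.0 to below 30.0. Nothing bars diabetes at BMI 30-45. The diabetes-specific exclusion is HbA1c of 8.0% or higher. The medication exclusions begin with "Regular use of growth hormone, anabolic steroids/hormones, sex steroids" and go on to corticosteroids, osteoporosis drugs, protein supplements and weight-loss medications or procedures. Insulin and other glucose-lowering drugs are not named.

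**Analysis.** The protocol's Data analysis section analyses all randomised participants by assigned group. Cardiometabolic outcomes at 6 and 18 months use a repeated-measures ANCOVA, and "All models will be adjusted for the baseline measure, age, gender, and race". Other influences on response may be taken up in secondary analyses; the examples given do not include medication.

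**Medication data.** Under Descriptive variables and potential covariates: "We will record medication and supplement use at baseline and at 6-, 12- and 18-month follow-up". Participants bring their medicines for review, and "The medication form will specifically ask about the use of protein supplements, anti-inflammatory agents, and sex steroids or corticosteroids". Glucose-lowering drugs are not one of the form's named items.

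**SAP.** It covers bone outcomes only and does not mention glucose, insulin or HOMA.

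**The concern.** HOMA is meaningful only when the fasting insulin reading reflects the participant's own secretion. In an insulin user the reading may include injected drug, and it can then move with dose. Adjusting for the baseline value does not cure this, because the dose can change between visits. The plan targets roughly 10 kg of weight loss, so changes in glucose-lowering treatment during follow-up are plausible. A few extreme values could widen the standard error of the HOMA and fasting-insulin contrasts, and a between-arm difference in treatment changes could shift them.

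The label is a separate and simpler problem. The formula multiplies insulin by glucose, so it rises as resistance rises. A reader who takes the protocol's word sensitivity literally would reverse the direction of an effect. The paper that the protocol cites for the formula has insulin resistance in its own title.

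**Working it through.** The documents give no sample size, power, SD or effect size for glucose, insulin or HOMA, so there is no planned figure to reproduce. The number of insulin users is also not given. Every user share and SD below is an assumption.

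**1. Can insulin users be in the analysis?** Diabetes below HbA1c 8.0% is eligible, insulin is not an excluded drug, HOMA has no treatment restriction, and all randomised participants are analysed. Together these provisions allow it. None reports that it occurred.

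**2. How far can one value move?** Take two illustrative readings:
- insulin 10, glucose 5.5: 10 × 5.5 / 22.5 = 2.4
- insulin 60, glucose 7.5: 60 × 7.5 / 22.5 = 20.0

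**3. Added noise, log scale.** Let p be the share of insulin users, s0 the residual SD of log-HOMA change in non-users and s1 that in users. Then variance = (1 − p)·s0² + p·s1², the factor for required n is variance / s0², and the factor for the standard error is its square root. Assume s0 = 0.35 and s1 = 0.7 to 1.0.

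For p = 0.05:
- s1 = 0.7: 0.95 × 0.1225 + 0.05 × 0.49 = 0.1409; / 0.1225 = 1.15; square root 1.07
- s1 = 1.0: 0.95 × 0.1225 + 0.05 × 1.00 = 0.1664; / 0.1225 = 1.36; square root 1.17

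| Share of users | Users per arm at n = 60 | Required-n factor | Standard-error factor |
|---|---|---|---|
| 2% | about 1 | 1.06-1.14 | 1.03-1.07 |
| 5% | 3 | 1.15-1.36 | 1.07-1.17 |
| 10% | 6 | 1.30-1.72 | 1.14-1.31 |

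**4. Added noise, raw scale.** Assume SD of HOMA change 2 in non-users and 6 to 10 in users. The standard-error factor is √{[(1 − p)·4 + p·s²] / 4}.
- p = 0.03: √1.24 = 1.11 to √1.72 = 1.31
- p = 0.05: √1.40 = 1.18 to √2.20 = 1.48
- p = 0.08: √1.64 = 1.28 to √2.92 = 1.71

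At 5% of the 187 enrolled, 0.05 × 187 = 9.4 people, about 3 per arm.

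**5. Possible bias in the contrast.** If treatment changes make insulin users in two arms differ by 0.25 to 0.5 log units, the arm difference shifts by p times that amount. This runs from 0.02 × 0.25 = 0.005 to 0.10 × 0.5 = 0.05. For comparison, the difference detectable with 80% power at two-sided α = 0.05, without correction for three comparisons, is (1.96 + 0.84) × 0.35 × √(2/n). That is 0.18 at n = 60 and 0.20 at n = 50 per group. The shift is at most about 0.05 / 0.18 = 28% of the detectable difference, and usually far less.

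**The case against.** Several points weigh against making much of this.

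- HOMA is tertiary, and the Data analysis section treats cardiometabolic factors as exploratory. The SAP for this ancillary study does not use them. This stands.
- Insulin-treated participants are an inference from the entry criteria. The Medical Director must approve each participant, and uncontrolled metabolic disease is excluded, so there may be very few or none. This stands, and it is why every size above is conditional.
- Medication use sits under a heading that includes potential covariates, and the list of factors for secondary analysis is open. Adjustment is therefore possible. It is not pre-specified, and a medication covariate would not make HOMA valid in someone injecting insulin.
- The protocol's Database management section provides for outlier checks and for transformations where needed. This favours the smaller log-scale figures but does not settle whom to include.

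A reader might infer that these outcomes measure drug changes rather than diet, or that unequal drug reduction would mask a true glycaemic benefit. The documents do not support that. Assignment is randomised, the diets are isocaloric, and every arm has the same calorie deficit and exercise programme, so weight-loss-driven drug changes are expected in all arms. If one diet does lead to less drug use, an intent-to-treat contrast legitimately compares the arms under the treatment actually received. Nor is it established that a few insulin users would dominate the HOMA result; only the upper end of the assumed raw-scale range comes near that.

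**Conclusion.** The point holds as a gap in the definition of two exploratory outcomes. As written, HOMA would be calculated and analysed for any insulin user the entry criteria admit, where it does not estimate that person's own insulin physiology. The sensitivity label also has the wrong direction.

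The main expected consequence is lost precision: at 5% users, a standard error 1.07 to 1.17 times larger on the log scale or 1.18 to 1.48 times on the raw scale. Bias in the arm contrast is possible but smaller, 0.005 to 0.05 log units against a detectable 0.18 to 0.20. All of these sizes rest on assumed shares and SDs; with no insulin users the effect is nil, and only the label needs correcting. The primary and secondary conclusions do not depend on it. This is a low-priority improvement.

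**What to change.** - Analyse fasting insulin and HOMA in participants not using insulin at baseline, identified from the baseline medication review. This restriction is fixed before randomisation, so the randomised comparison is preserved within the subset.
- Describe HOMA as an index of insulin resistance, with higher values meaning more resistance.
- Tabulate by arm any start, stop or change of glucose-lowering treatment after randomisation, from the reviews already planned at 6, 12 and 18 months. Because the form does not name these drugs, derive the flag from the medication inventory.
- If an analysis excluding participants with such changes is wanted, present it as a supportive sensitivity analysis only. It conditions on a post-randomisation event that may itself follow from the diet.

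The cost is a few sentences, one derived flag and a slightly smaller set for these two outcomes, whose results would then apply to people not using insulin at entry. The baseline restriction does not remove someone who starts insulin later; the table by arm shows whether that matters. The rule should be written before the glycaemic results are examined.

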Our **primary goal** is to determine the effect of a higher protein (1.2 g/kg body wt/d; ~30% of energy) / lower carbohydrate (CHO; 40-45% of energy) diet during a 6-month weight loss intervention in obese older adults on physical function compared with an isocaloric lower protein (current RDA of 0.8 g/kg body wt/d; 15-20% of energy) / higher CHO (55-60% of energy) diet, and whether continuing a higher protein / lower CHO diet following weight loss results in better maintenance of physical function. This will be accomplished with an 18-month randomized trial in 225 obese (BMI 30-45 kg/m² or 27-30 kg/m² with 1 additional risk factor), older (65-85 years) men and women at risk for disability (expSPPB <2.50). All participants will undergo a 6-month weight loss intervention of caloric restriction and exercise followed by 12 months of follow-up with randomization to one of three groups (n=75/group): 1) Lower protein / higher CHO diet for the 6-month weight loss and 12-month follow-up phases (RecProt); 2) Higher protein / lower CHO diet for the 6-month weight loss phase only (6-mo HiProt); or 3) Higher protein / lower CHO diet for the 6-month weight loss and 12-month follow-up phases (18-mo HiProt).

Primary Aim: To determine the effects of a higher protein / lower CHO diet vs. lower protein / higher CHO diet during a 6-month weight loss intervention and 12 months of follow-up on 18-month physical function assessed by the expanded Short Physical Performance Battery (primary outcome) and muscle strength.

Hypothesis: Participants randomized to a higher protein diet during weight loss and follow-up (18-mo HiProt) will have greater improvements in physical function than participants randomized to a higher protein diet during weight loss only (6-mo HiProt), followed by those randomized to a lower protein diet (RecProt).

Secondary Aim: To determine the effects of a higher protein / lower CHO diet vs. lower protein / higher CHO diet during a 6-month weight loss intervention and 12 months of follow-up on 18-month body weight and body composition.

Hypothesis: Participants randomized to a higher protein diet during weight loss and follow-up (18-mo HiProt) will have better weight loss maintenance, lower fat-to-lean mass ratio, greater thigh muscle volume, and lower inter-muscular adipose tissue than participants randomized to a higher protein diet during weight loss only (6-mo HiProt), followed by those randomized to a lower protein diet (RecProt).

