Sample size: The sample size chosen for this study (n=225; 75/group) will provide $\geq 80\%$ power ($\alpha=0.05$) to detect clinically meaningful effects of a higher protein / lower CHO diet during weight loss and follow-up on physical function (with estimated retention of 80% or 60 completers per group; see **Table 3**). Baseline standard deviations and pre-post correlations used for power analyses were calculated using data from obese older adults from our OPTIMA study¹¹ – a weight loss study with the same inclusion/exclusion criteria as the proposed study. Standard deviations were assumed to be similar between groups. The mean group differences we can detect correspond to an absolute change from average baseline values of these measures in obese older adults of 0.2 points for the expSPPB and 12.6 Nm for muscle strength. Differences of 0.12 points and 0.22 points on the expSPPB have been shown to be small and large clinically meaningful differences, respectively.⁶³ Even with a conservative drop-out rate of 20%, 60 participants/group provides $\geq 80\%$ power (overall $\alpha=0.05$, 2-sided tests for 3 comparisons) to detect between group differences for primary and secondary outcomes over 18 months. In response to our NIA-appointed DSMB, we have recalculated the power based on the actual number of participants enrolled (total n=187 or ~ 50 per group after accounting for the 20% drop-out rate) using the same baseline standard deviations and pre-post correlations from obese older adults in our OPTIMA study noted above.

Table 3. Power to detect significant differences in mean change between groups with ANCOVA ($\alpha=0.05$ after Bonferroni correction for each outcome; 2-sided test), assuming similar SD between groups

Outcome measure	Group Comparison	Pre-Post Correlation	Standard Deviation (SD)	Mean group difference	Effect Size (diff/SD)	Power for Analysis of Covariance (n per group)			
						n=60	n=65	n=75	n=50
ExpSPPB (points)	RecProt vs. 6mo HiProt	0.72	0.5	0.20	0.41	80	84	89	71
	6mo vs. 18mo HiProt			0.20	0.41	80	84	89	71
	RecProt vs. 18mo HiProt			0.41	0.82	>99	>99	>99	>99
Knee extensor strength (Nm)	RecProt vs. 6mo HiProt	0.77	32.8	12.6	0.38	81	84	90	72
	6mo vs. 18mo HiProt			12.6	0.38	81	84	90	72
	RecProt vs. 18mo HiProt			25.3	0.77	>99	>99	>99	>99
Lean mass (Kg)	RecProt vs. 6mo HiProt	0.99	12.0	1.1	0.09	86	89	93	78
	6mo vs. 18mo HiProt			1.1	0.09	86	89	93	78
	RecProt vs. 18mo HiProt			2.2	0.18	>99	>99	>99	>99

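### For the three pairwise expSPPB contrasts the only stated multiplicity rule is a plain Bonferroni; with three arms, Shaffer's procedure keeps 5% family-wise control within each outcome and rejects at least as much

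*Protocol*

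**What the plan says.** The Sample size paragraph of the protocol's Analytical Plan sets an overall alpha of 0.05 with "2-sided tests for 3 comparisons". The Table 3 caption says that significance is judged "after Bonferroni correction for each outcome; 2-sided test), assuming similar SD between groups". For expSPPB, Table 3 gives each adjacent contrast (RecProt vs 6-mo HiProt, and 6-mo vs 18-mo HiProt) 80%, 84% and 89% power at 60, 65 and 75 per group. A column added at the DSMB's request, after enrolment of 187, gives 71% at 50 per group. The extreme contrast, RecProt vs 18-mo HiProt, is above 99% throughout.

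The Data analysis paragraph says only: "Group contrasts will be constructed and tested within each model". It names no adjustment and no order of testing.

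The primary hypothesis under Objectives is an ordering: the 18-month higher-protein arm "will have greater improvements in physical function than participants randomized to a higher protein diet during weight loss only (6-mo HiProt), followed by" the lower-protein arm.

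The SAP covers the ancillary bone outcomes, with its own alpha of 0.025. It gives no rule for expSPPB.

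**The concern.** Plain Bonferroni treats the three pairwise nulls as if any combination of them could be true. With three arms that is impossible: if two pairs of arms are equal, so is the third. Ignoring this costs power on the two adjacent contrasts, which are the ones that the enrolment shortfall took below 80%.

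Those contrasts carry information that the extreme contrast cannot. RecProt vs 18-mo HiProt does not show whether continuing higher protein after weight loss adds anything, and that question is part of the stated primary goal. With 50 completers per arm, the adjacent difference detectable with 80% power under Bonferroni is 0.227 points. The protocol itself calls 0.22 points a large meaningful difference.

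**Working it through.** **Inputs** (protocol, Sample size and Table 3): SD 0.5; pre-post correlation 0.72; adjacent effect size 0.41, so a difference of 0.41 × 0.5 = 0.205 (printed as 0.20; the extreme difference of 0.41 is twice 0.205); three two-sided contrasts; 187 enrolled with 20% drop-out, so 187/3 × 0.8 = 49.9, about 50 per arm.

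**Reproducing Table 3.** Residual SD = 0.5 × √(1 − 0.72²) = 0.347. At n = 50 the standard error of a contrast is 0.347 × √(2/50) = 0.0694, and 0.205/0.0694 = 2.95. Normal-approximation power at 0.05/3 = 0.0167 per test:

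| n per arm | 60 | 65 | 75 | 50 |
|---|---|---|---|---|
| Table 3 | 80 | 84 | 89 | 71 |
| Recomputed | 80.0 | 83.5 | 89.0 | 71.2 |

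At n = 50, alpha 0.025 would give 76.2% and alpha 0.05 would give 84.0%. The table is therefore a three-way Bonferroni. (With 0.20 in place of 0.205, the n = 50 figure is 68.7%.)

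**Why the step-down is valid.** Any two of the pairwise nulls imply the third, so only three states are possible: all three nulls true, exactly one true, or none true. Closed testing then needs two conditions to reject a contrast. The global null must be rejected, which happens when the smallest p-value is at most 0.05/3. The contrast's own p-value must also be at most 0.05. A contrast with p ≤ 0.05/3 meets both conditions, so every Bonferroni rejection is kept.

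**Power at n = 50** (simulated t-tests with 146 degrees of freedom; t-based figures run about one point below the normal approximation under Bonferroni):

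| Arm effects: RecProt / 6-mo / 18-mo | Quantity | Bonferroni | Shaffer |
|---|---|---|---|
| 0 / 0.205 / 0.41 (Table 3) | each adjacent contrast | 70.2% | 83.5% |
| same | both adjacent contrasts | 44% | 67.5% |
| 0 / 0.205 / 0.205 or 0 / 0 / 0.205 | each true contrast | 70% | 78% |
| 0 / 0.205 / 0.3075 | RecProt vs 6-mo | 70% | 83% |
| same | 6-mo vs 18-mo | 18% | 31% |
| 0 / 0.11 / 0.22 | each adjacent contrast | 20% | 33% |
| same | both adjacent contrasts | 1% | 6% |

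With the rounded step of 0.20, each adjacent contrast goes from 68% to 82%. Knee extensor strength (SD 32.8, correlation 0.77, step 12.65, half of the tabulated 25.3) goes from 72.5% to 85.1%.

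**Equivalents in size.** Once the first rejection has been made, the difference detectable with 80% power at n = 50 falls from 0.227 to 0.196 points. For 84% power per adjacent contrast, 66 completers per arm are needed at 0.05/3 and 51 at 0.05.

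**Family-wise error.** Under the global null it is 4.3% for both rules. With one true null and the third arm different, it is 1.7% for Bonferroni and 4.9-5.0% for Shaffer.

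**The case against.** Bonferroni is a valid, conservative choice. It appears only in the power section, where it need not bind the analysis, so there is no error to correct. That stands: this is a loss of efficiency, not a flaw in validity. It does leave the analysis paragraph without any rule, so one has to be written there in any case.

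A reader might infer that power rises from 71% to 84% whatever the truth. The documents do not support that. The figure rests on Table 3's additive effects, under which RecProt and 18-mo HiProt differ by 0.41 points, nearly twice the protocol's large difference, so the first rejection is almost certain. At 0/0.11/0.22 the adjacent contrasts remain poorly powered under either rule.

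A reader might also infer that the primary hypothesis fails unless both adjacent contrasts are significant. The protocol states an expected ordering but no such criterion, and the extreme contrast keeps more than 99% power at n = 50. The joint figures are descriptive.

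Three further points stand as limits. The supplied protocol is the parent study's, and the only SAP is for the bone study, so whether a separate parent SAP fixes the procedure cannot be judged. The shortfall was known when the n = 50 column was added, so a move to a more powerful rule needs a dated, blinded justification. Shaffer also uses up slack that Bonferroni leaves: expSPPB and muscle strength both sit in the primary aim, and neither rule controls error across the two.

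Holm's procedure is a simpler alternative. It reaches 82.6% per adjacent contrast under Table 3's effects, but 73% against Shaffer's 78% when two arms are equal.

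**Conclusion.** The point holds as an efficiency gain that needs no further participants. The only stated rule for the three expSPPB contrasts is Bonferroni at 0.05/3. In a three-arm trial Shaffer's procedure never rejects less and keeps strong 5% control within the outcome. At about 50 completers per arm it is worth about 13 percentage points per adjacent contrast if Table 3's SD, correlation and additive effects are right. It is worth about 8 points per true contrast if two arms are equal. At 0/0.11/0.22 it adds about 13 points, from a low base of about 20%.

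**What to change.** By a dated amendment made before unblinding, add to the Data analysis paragraph (nothing there needs replacing):

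> For each outcome the three pairwise contrasts are tested by Shaffer's procedure: if the smallest p-value is ≤0.0167, that contrast is significant and the other two are each tested at two-sided 0.05; otherwise none is significant.

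Align the Table 3 caption with this. Recompute the n = 50 column under the rule, state the assumed arm effects, and show at least one non-additive alternative beside them. The probability that both adjacent contrasts succeed would be a useful extra line, labelled as descriptive.

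The drafting cost is one sentence and one table column, plus the documented blinded rationale. The amendment should state the downsides. Simultaneous confidence intervals will not match the test exactly; ordinary 95% intervals can be reported beside adjusted p-values, but one of them may exclude zero where the adjusted test does not reject. Family-wise error with one true null rises from 1.7% to the nominal 5%. Control remains within each outcome, not across expSPPB and strength. The documents do not show whether unblinding has already taken place. If it has, the rule can no longer be presented as prespecified.
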